21. APPENDICES

i.

APPENDIX 1- LIST OF NON-RECOMMENDED TREATMENTS FOR CMT1A PATIENTS

- ✓ **Baclofen** (Liorésal[®]), **naltrexone** (Nalorex[®], Revia[®]) **sorbitol** (pharmaceutical form, such as sorbitol Delalande[®], Hépargitol[®], Microlax[®], Schoum[®]...) **and ascorbic acid** (vitamin C[®], Laroscorbine[®]...), as they may interfere with study treatment evaluation.
- ✓ **Levothyroxin** (Levothyrox[®], L-Thyroxin serb[®]) as it may confound biomarkers analysis.
- ✓ **Opioid analgesics** (morphine, fentanyl, hydromorphone, oxycodone, buprenorphine, nalbuphine, Lamaline[®] and tramadol – including Ixprim[®], Topalgie[®], Contramal[®] and Zalduar[®]) and **other drugs of the opioid class such as methadone** because of their potential interaction with naltrexone.
- ✓ **Codeine** is allowed only at doses of ≤ 20 mg per unit dose; analgesics such as **Efferalgan** **Codeine**[®] are therefore not allowed as they contain 30 mg codeine per unit dose.
- ✓ **Levodopa** (Sinemet[®], Modopar[®], Stalevo[®]...) should not be used as in combination with baclofen there may be increased adverse effects such as confusion, agitation and hallucinations.
- ✓ **Centrally acting antihypertensive drugs such as clonidine** (Catapressan[®]), **methyldopa** (Aldomet[®]), **moxonidine** (Physiotens[®]), and **rilmenidine** (Hyperium[®]), as baclofen may increase their antihypertensive effect (risk of hypotension).
- ✓ Other classes of antihypertensive compounds are allowed, but physicians should be aware of a potential increased antihypertensive effect on combined treatment with baclofen.
- ✓ Potent central nervous system (CNS) depressants such as **barbiturates, benzodiazepines, and neuroleptics** are not allowed because of potential increase in side effects in association with baclofen.
- ✓ **Clonazepam** (Rivotril[®]) can however be used at low daily doses (≤ 20 drops/day, i.e. 2 mg/day).
- ✓ Treatments that may induce or aggravate peripheral neuropathies are also forbidden during the trial, such as the **antiepileptic drug phenytoin** (Di-Hydant[®]) and anticancer drugs such as **vincristine, vinblastine, cisplatin, carboplatin, oxaliplatin, taxol**.
- ✓ Antiepileptic drugs such as **valproate** (Depakine[®] or Depakote[®]), **carbamazepine** (Tegretol[®]), oxcarbazepine (Trileptal[®]), **gabapentine** (Neurontin[®]), **pregabalin** (Lyrica[®]) can be used but should be maintained at constant doses throughout the trial.
- ✓ **Antidepressant drugs** including **imipraminic antidepressants** can be used, but they should be maintained at constant doses throughout the trial, as imipraminic antidepressant can potentiate the hypotonia induced by baclofen, and sedative antidepressants may potentiate CNS depression.
- ✓ Drugs which could induce neuropathies:
 - Anti-cancer drugs: vincristine, vinblastine, cisplatin, carboplatin, paclitaxel;
 - Anti-infectious: metronidazole, nitrofurantoin, chloramphenicol;
 - Anti-leprosy drug: dapsone;
 - Anti-tuberculosis drug: isoniazid;
 - Anti-retroviral drugs: didanosine (DDI), zalcitabine (DDC);
 - Anti-arythmic drugs: amiodarone;
 - Anti-inflammatory drugs (disease-modifying therapy): gold salts;
 - Alcoholic detoxification: disulfiram;
 - Anti-epileptic drugs: phenitoin;
 - Others: alcohol, pyridoxin(Vit B6) at very high dose;

ii.

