Investigational treatments	
PXT3003 is a fixed dose combination of RS-baclofen, naltrexone hydrochloride and D-sorbitol. Two doses of PXT3003 will be tested:
 
Dose 1 = 3 mg baclofen, 0.35 mg naltrexone and 105 mg sorbitol given twice daily;
 
Dose 2 = 6 mg baclofen, 0.70 mg naltrexone and 210 mg sorbitol given twice daily;
 
The control group will be matching placebo.
 
Patients will be randomized in 3 groups in order to receive either PXT3003 at one of the 2 different doses or placebo.
 
PXT3003 and placebo will be supplied as 100 mL clear oral solution in amber glass bottle (for 10 days of treatment) which will be delivered with a plastic adapter and an adaptable plastic pipette for medication dispensation which will be graduated with a 5 ml graduation corresponding to the full dose and 2.5 mL for the half-dose of medication to be administered. Each strength of PXT3003 corresponding to one of the tested dose levels and the placebo will have the same presentation and taste.
 
PXT3003 and placebo will be provided in carton boxes of 4 bottles.
 
The study drug (PXT3003 or matching placebo) will be administered per oral route 5 ml twice daily (morning and evening with food) for 15 months.
 
To improve tolerability, treatment should start progressively (for all randomized patients): half dose (2.5 mL of the liquid formulation) will be administered twice a day during the two first weeks and then will be increased to the full dose (5 mL of the liquid formulation) twice a day until the end of study treatment.

Concomitant treatments	
Authorized treatments:
 
Standard care for CMT1A, particularly occupational and physical therapy or drugs for pain (excluding opioids and benzodiazepines) are authorized and should be reported in the CRF;
 
Prohibited treatments:
 
 - High doses of Ascorbic acid (\geq1 g/day) - Levothyroxine;

Concomitant treatments (con't)	
 - Baclofen, naltrexone, and sorbitol in their current pharmaceutical forms at full dose. The use of opiates, and potentially neurotoxic drugs should also be avoided. 
A list of non-recommended treatments is provided in protocol section 21.

Primary efficacy endpoint	Improvement of disability measured by the Overall Neuropathy Limitation Scale (ONLS) score.

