Consequently careful titration of dosage from 5 mg t.i.d. to 20 mg q.i.d. is recommended until the patient is stabilized. This is particularly relevant if the patient is ambulant in order to minimize muscle weakness in the unaffected limbs or where spasticity is necessary for support. The incidence of adverse effects during oral administration of baclofen can be however reduced by slowly increasing the dose to optimal therapeutic levels.

Baclofen may increase the sedative effect of alcohol and CNS depressants such as barbiturates, opioids, benzodiazepines and other anxiolytic drugs, hypnotics, neuroleptics, antihistamine H1 compounds, centrally acting antihypertensive drugs, sedative antidepressants. Baclofen may increase the side effects of levodopa (confusional state, agitation, hallucinations) and the antihypertensive effect of antihypertensive compounds. Baclofen may induce increase hypotonia if co-administered with tricyclic antidepressants.

However, taking in account the low doses of baclofen in PXT3003, the warnings described can be nuanced.

Naltrexone current product labelling in its approved indication for opioid and alcohol dependence specifies that the most frequent adverse effects reported with naltrexone are gastrointestinal effects; these can be minimized by taking the drug with a meal, and are not likely to occur at the low doses administered in PXT3003.

Naltrexone is contraindicated in particular in patients with acute hepatitis or liver failure, currently dependent on opioids or in conjunction with an opioid containing medication, who have demonstrated hypersensitivity to naltrexone hydrochloride and who have severe renal failure.

In alcohol dependence, naltrexone even at high daily dose (much higher than the very low dose used in PXT3003) is considered as a safe medication. Control of liver values prior to initiation of treatment is however recommended, as naltrexone has been reported to induce dose-related hepatotoxicity. However, evidence of hepatotoxic risk has not been demonstrated at the doses usually recommended, and it should thus be of no relevance for the low doses administered in PXT3003.

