9.2 Exclusion criteria

Patients who have met all the above inclusion criteria listed will be screened for the following exclusion criteria:

- 1- Any other associated cause of peripheral neuropathy such as diabetes;
- 2- Patients with another significant neurological disease or a concomitant major systemic disease;
- 3- Clinically significant history of an unstable medical illness since the last 30 days (unstable angina, cancer...) that may jeopardize the participation in the study;
- 4- Significant hematologic disease, hepatitis or liver failure, renal failure;
- 5- Limb surgery within six months before randomization or planned before completion of the trial;
- 6- Clinically significant abnormalities at the pre-study clinical examination, routine laboratory evaluations and electrocardiogram (ECG);
- 7- Elevated AST/ALT (>3 x ULN) and/or elevated serum creatinine levels (>1.25 x ULN);
- 8- History of recent alcohol or drug abuse or non-adherence with any treatment or other experimental protocols;
- 9- Patients using unauthorized concomitant treatments including but not limited to baclofen, naltrexone, sorbitol (pharmaceutical form), opioids, levothyroxin and potentially neurotoxic drugs such as amiodarone, chloroquine, cancer drugs susceptible to induce a peripheral neuropathy; (list provided in appendix 1). Patients who can/agree to stop these medications 4 weeks before randomization and during the whole study duration can be included;
- 10- Women of child bearing potential not using highly-effective method(s) of birth control (ie, with low failure rate <1% per year) throughout the study and/or unwilling to be tested for pregnancy; Pregnancy or breast feeding;
- 11- History of safety issues or known hypersensitivity to baclofen, naltrexone or sorbitol, or to any of the individual components of PXT3003;
- 12- Any contraindication to use of baclofen (e.g. porphyria), naltrexone or sorbitol as defined in the national product labels;
- 13- Suspected inability to complete the study follow-up (transient visitors, tourists or any patient for whom the follow-up evaluation would be too difficult to appreciate for any reason);

- 14- Limited mental capacity or psychiatric disease rendering the subject unable to provide written informed consent or comply evaluation procedures;
- 15- Patients who have participated in another trial of investigational drug(s) within the past 30 days;

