9.3.1 Authorized concomitant treatments

PXT3003 will be administered on top of standard of care (SOC) consisting of supportive therapies such as pain killers (except neurotoxic drugs or opiates), physiotherapy, occupational therapy, and orthopedic devices that will be authorized during the entire study.

All concomitant treatment should be reported in the CRF.

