9.3.2 Forbidden concomitant treatments

The following concomitant treatments are forbidden within 30 days before randomization and during the whole study:

- High doses of Ascorbic acid (≥ 1 g/day)
- Levothyroxin are forbidden.
- Baclofen, naltrexone, and sorbitol in their current pharmaceutical forms at full dose are forbidden.

The use of opiates, such as morphine, fentanyl, oxycodone, buprenorphine, nalbuphine, tramadol, and methadone potentially neurotoxic drugs should also be avoided. A list of non-recommended treatments is provided in Appendix 1.

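### The protocol contradicts itself on codeine: it is barred as an opioid in the main text, allowed in Appendix 1, and in conflict with the naltrexone contraindication reported in section 6.5

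*Combined protocol and SAP*

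**What the plan says.** Opioids are addressed in several places:

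- Section 9.2, exclusion criterion 9 (also in the synopsis) begins "Patients using unauthorized concomitant treatments including but not limited to baclofen, naltrexone, sorbitol (pharmaceutical form), opioids, levothyroxin". It cites Appendix 1 as its list and admits users only if they stop these drugs 4 weeks before randomization and throughout the study.
- The synopsis, under concomitant treatments, states that "drugs for pain (excluding opioids and benzodiazepines) are authorized".
- Section 9.3.1 authorizes "supportive therapies such as pain killers (except neurotoxic drugs or opiates").
- Section 9.3.2, which is headed as the list of forbidden treatments, says that opiates and "potentially neurotoxic drugs should also be avoided". Its examples of opiates do not include codeine.
- Appendix 1 bars opioid analgesics because they may interact with naltrexone. Its next bullet says that codeine "is allowed only at doses of ≤ 20 mg per unit dose".

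Two further places concern naltrexone. Section 6.5, describing current product labelling, says that naltrexone is contraindicated in patients "currently dependent on opioids or in conjunction with an opioid containing medication". Exclusion criterion 12 in section 9.2 excludes "Any contraindication to use of baclofen (e.g. porphyria), naltrexone or sorbitol as defined in the national product labels".

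**The concern.** Consider a patient who takes a codeine product within the Appendix 1 limit. Under the opioid wording of criterion 9 the drug must be stopped. Under section 9.3.1 it is not an authorized pain killer. Under Appendix 1 it may continue. If it continues, the patient takes naltrexone together with an opioid-containing drug, which is the combination that section 6.5 reports as contraindicated in the labelling.

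Two things are at stake. One is safety: the protocol carries an allowance that collides with a contraindication it reports, and gives no explanation. The other is classification. Section 14.1 removes patients with a major protocol violation from the per-protocol set, and section 11.4 lets a major deviation lead to withdrawal from the study. Whether low-strength codeine counts as either depends on which page is read.

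**Working it through.** No arithmetic applies, so the check is a comparison of the texts. That codeine belongs to the opioid class follows from its position in Appendix 1, directly after the opioid bullet and as a limited exception to it.

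| Place | Status of codeine as an opioid or opiate | Refers to Appendix 1? |
|---|---|---|
| Exclusion criterion 9 | Must be stopped; no dose exception | Yes |
| Synopsis, concomitant treatments | Not authorized; no exception | Yes, through section 21 |
| Section 9.3.1 | Not authorized; no exception | No |
| Section 9.3.2 | To be avoided, under a heading of forbidden treatments; codeine not named | Yes |
| Appendix 1 | Allowed within a unit-dose limit | – |
| Section 6.5 | Use with an opioid-containing drug reported as contraindicated | No |
| Exclusion criterion 12 (section 9.2) | Labelled naltrexone contraindications exclude | No; refers to national labels |

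**Step 1: can Appendix 1 govern?** Where a section refers to the appendix, its codeine bullet can be read as a listed exception to the general bar. That covers criterion 9, the synopsis cell and section 9.3.2. Section 9.3.1 has no such reference and excludes opiates outright.

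**Step 2: does the exception survive section 6.5 and criterion 12?** Section 6.5 uses the low doses in PXT3003 to play down the baclofen warnings, the gastrointestinal and liver effects of naltrexone, and the bowel effects of sorbitol. It says nothing of the kind about naltrexone with opioids. Its general statement that lower doses should not alter the risk/benefit balance does not mention opioid co-medication either. Appendix 1 also gives the naltrexone interaction as its reason for barring opioids in this trial, so the protocol treats the interaction as relevant at the trial's doses.

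**Step 3: is criterion 12 consistent across the document?** The synopsis version names only porphyria, as a contraindication to baclofen. The version in section 9.2 extends to naltrexone and sorbitol labels. A reader of the synopsis alone would miss the naltrexone route to exclusion.

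**Step 4: related wording.** Two smaller mismatches sit in the same sections:

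- The synopsis leaves benzodiazepines out of the authorized pain drugs. Appendix 1 bars the class but makes an explicit exception for low-dose clonazepam.
- Potentially neurotoxic drugs are to be avoided in section 9.3.2, while Appendix 1 forbids treatments that may induce or aggravate neuropathy. The appendix as a whole is titled as a list of non-recommended treatments.

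**The case against.** The strongest reply is that this is a general rule with a listed exception. Criterion 9, section 9.3.2 and the synopsis all send the reader to Appendix 1, so a site that follows section 9.2 should arrive at the codeine bullet. That stands for those three places. It does not reach section 9.3.1, section 6.5 or criterion 12.

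A second reply is that section 6.5 describes labelling for the approved indication, whereas it puts naltrexone in PXT3003 at 1/35 of the recommended dose. This is fair as far as it goes. The labels themselves are not in the documents, and the protocol does not say outright that its own combination is contraindicated. But it offers no reasoning that sets this contraindication aside, and criterion 12 turns label contraindications into exclusions without a dose qualification.

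Several stronger readings are tempting but not supported:

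- **Clonazepam is equally contradictory.** Criterion 9 does not name benzodiazepines, sections 9.3.1 and 9.3.2 do not mention them, and Appendix 1 states its exception openly. The only tension is a parenthesis in the synopsis.
- **Section 9.3.2 adds a third status.** Its softer verb sits under a heading of forbidden treatments and is better read as loose wording.
- **The unit-dose limit is itself an error because it sets no daily ceiling.** That would be a criticism of a clinical rule, not a contradiction in the text.
- **Enrolment can still be corrected.** This version is dated December 2017 and the synopsis planned recruitment to end in Q4 2016. On those dates, mainly on-study use and per-protocol classification remain open.

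**Conclusion.** The contradiction on codeine is real and should be resolved. Appendix 1 allows what section 9.3.1 does not authorize, and the allowance conflicts with section 6.5 and, through it, with criterion 12. The step from section 6.5 to criterion 12 assumes that the national labels carry the contraindication as section 6.5 reports it. The clonazepam and neurotoxic-drug mismatches are minor.

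The size cannot be given as a number of patients: the documents report no codeine use and offer no basis for assuming a rate. A reader might infer that the primary result is threatened. It is not directly, because section 14.1 runs the efficacy analyses on all randomized patients and repeats them on the per-protocol set only as a sensitivity check. The consequences are for safety during treatment and for who belongs in the per-protocol set.

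**What to change.** Reconcile exclusion criteria 9 and 12 (including the synopsis version of 12), sections 6.5, 9.3.1 and 9.3.2, the synopsis cell on concomitant treatments, and Appendix 1. For opioids including codeine, benzodiazepines including clonazepam, and neurotoxic drugs, state one entry status and one on-study status, and use one term for each level of restriction. The sponsor's medical team should settle the codeine allowance against the contraindication reported in section 6.5 and record the reason; no clinical rule or dose is proposed here.

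Then state in the analysis plan which uses of these drugs count as major violations, and classify each patient's recorded medication against that single rule, blind to treatment, when the per-protocol set is fixed. Section 9.3 already requires name, dosage, route and dates of every concomitant treatment in the case report form, so no new data are needed. The cost is an amendment to the text and a blinded review of medication. The small downside is that some patients may be reclassified as deviations.

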APPENDIX 2- ONLS

Name:
Date:

Overall Neuropathy Limitations Scale (ONLS)

Instructions: The examiner should question **and** observe the patient in order to determine the answers to the following questions. Note should be made of any other disorder other than peripheral neuropathy which limits function at the foot of the page.

ARM SCALE

Does the patient have any symptoms in their hands or arms, eg tingling, numbness or weakness? Yes No
(if "no", please go to "legs" section)

Is the patient affected in their ability to:

	Not affected	Affected but not prevented	Prevented
Wash and brush their hair			
Turn a key in a lock			
Use a knife and fork together (or spoon, if knife and fork not used)			
Do or undo buttons or zips			
Dress the upper part of their body excluding buttons or zips			

If all these functions are prevented can the patient make purposeful movements with their hands or arms? Yes No Not applicable

Arm Grade

0=Normal

1=Minor symptoms in one or both arms but not affecting any of the functions listed
 2=Disability in one or both arms affecting but not preventing any of the functions listed
 3=Disability in one or both arms preventing at least one but not all functions listed
 4=Disability in both arms preventing all functions listed but purposeful movement still possible
 5=Disability in both arms preventing all purposeful movements

SCORE=_____**LEG SCALE**

	Yes	No	Not applicable
Does the patient have difficulty running or climbing stairs?			
Does the patient have difficulty with walking?			
Does their gait look abnormal?			
How do they mobilise for about 10 metres (ie 33 feet)?			
Without aid			
With one stick or crutch or holding to someone's arm			
With two sticks or crutches or one stick or crutch holding onto someone's arm or frame			
With a wheelchair			
If they use a wheelchair, can they stand and walk 1 metre with the help of one person?			
If they cannot walk as above are they able to make some purposeful movements of their legs, eg reposition legs in bed?			
Does the patient use ankle foot orthoses/braces? (please circle)			SCORE=_____

SCORE=_____**Leg grade**

0=Walking/climbing stairs/running not affected
 1=Walking/climbing stairs/running is affected, but gait does not look abnormal
 2=Walks independently but gait looks abnormal
 3=Requires unilateral support to walk 10 metres (stick, single crutch, one arm)
 4=Requires bilateral support to walk 10 metres (sticks, crutches, crutch and arm,frame)
 5=Requires wheelchair to travel 10 metres but able to stand and walk 1 metre with the help of one person
 6=Restricted to wheelchair, unable to stand and walk 1 metre with the help of one person, but able to make some purposeful leg movements
 7=Restricted to wheelchair or bed most of the day, unable to make any purposeful movements of the legs

Overall Neuropathy Limitation Scale=arm scale (range 0 to 5)+leg scale (range 0 to 7);
 (range: 0 (no disability) to 12 (maximum disability))

TOTAL SCORE=_____

Is there any disorder, other than peripheral neuropathy, which affects the above functions Yes No
 If yes please describe:

iii.

APPENDIX 3- CMTNS V2

Table 1. CMT neuropathy score – Version 2.

Parameter	0	1	2	3	4
Sensory symptoms*	None	Symptoms below or at ankle bones	Symptoms up to the distal half of the calf	Symptoms up to the proximal half of the calf, including knee	Symptoms above knee (above the top of the patella)
Motor symptoms (legs) [†]	None	Trips, catches toes, slaps feet Shoe inserts	Ankle support or stabilization (AFOs) Foot surgery [‡]	Walking aids (cane, walker)	Wheelchair
Motor symptoms (arms)	None	Mild difficulty with buttons	Severe difficulty or unable to do buttons	Unable to cut most foods	Proximal weakness (affect movements involving the elbow and above)
Pinprick sensibility ^{§,§}	Normal	Decreased below or at ankle bones	Decreased up to the distal half of the calf	Decreased up to the proximal half of the calf, including knee	Decreased above knee (above the top of the patella)
Vibration [¶]	Normal	Reduced at great toe	Reduced at ankle	Reduced at knee (tibial tuberosity)	Absent at knee and ankle
Strength (legs) ^{¶¶}	Normal	4+, 4, or 4– on foot dorsiflexion or plantar flexion	≤3 on foot dorsiflexion or ≤3 on foot plantar flexion	≤3 on foot dorsiflexion and ≤3 on plantar flexion	Proximal weakness
Strength (arms) ^{¶¶}	Normal	4+, 4, or 4– on intrinsic hand muscles ^{**}	≤3 on intrinsic hand muscles ^{**}	≤5 on wrist extensors	Weak above elbow
Ulnar CMAP (median)	≥6 mV (≥4 mV)	4–5.9 mV (2.8–3.9)	2–3.9 mV (1.2–2.7)	0.1–1.9 mV (0.1–1.1)	Absent (absent)
Radial SAP amplitude, antidromic testing	≥15 µV	10–14.9 µV	5–9.9 µV	1–4.9 µV	<1 µV

AFO, ankle-foot orthoses; CMAP, compound muscle action potential; SAP, sensory action potential.

*Use the picture below to discriminate the level of the symptoms.

†Uses aid *most of the time*. The patient was prescribed to wear/use or should be wearing/using the aid in the examiner's opinion (see written instructions, Table S2).

‡See written instructions for details of eligible foot surgery.

§Abnormal if patient says it is definitely decreased compared to a normal reference point.

¶Use Rydel-Seiffer tuning fork. Definition of normal: ≥5.

¶¶Limb strength scores refer to MRC grade.

**Intrinsic hand muscles strength assessment: test only abductor pollicis brevis (APB) and first dorsal interosseous (FDI), then choose the stronger to give the score.

[figure not shown]

Table 2. CMTNS spoken instructions.**Sensory loss**

Do you have loss of feeling anywhere in your feet or legs?

If so, does the loss of feeling extend above your toes?

Do they extend above the ankle?

Please identify the point on this drawing of the leg where the sensation becomes normal or nearly normal.

Are these symptoms constant (present all the time), present most of your daytime, less than one-half of the daytime, or just occasional? Daytime is defined as time between getting up and going to bed.

Motor symptoms (legs)

Do you have weakness in your legs or feet?

Do you ever trip over your toes/feet or turn or sprain your ankles?

Do your feet slap when you walk?

Do you wear shoe inserts/insoles (below the ankle)?

Do you wear braces, splints, or equivalent type of orthotics that extend above your ankle?

Have the above ankle orthotics described above ever been prescribed or suggested by healthcare professionals?

Have you had surgery on your feet or ankles?

If so, do you know if the surgery involved fusion of bones, a transfer of tendons, heel cord lengthening, or lowering of the arch?

Do you use a cane, stick, or walker to help you walk most of the time outside the home?

Do you use a wheelchair most of the time because of weakness?

Motor symptoms (arms)

Do you have difficulty with buttoning clothes (standard shirt buttons)?

If yes, are the difficulties mild or severe (severe includes unable)?

Can you cut most food including meat and pizza with normal utensils?

Do you have difficulty with activities that require extending or flexing your arms or activities using the upper arms?

iv.

